^a Participants who experience an acute infection or require additional time for scheduling screening procedures may extend the screening period beyond 35 days after consultation with the medical monitor, but not beyond a total of 56 days (8 weeks) from the signing of the informed consent. The screening visit window may also be extended up to 5 additional days to accommodate unanticipated delays in obtaining required screening results. An extension beyond 5 days will require approval by the Medical Monitor. Also, as the hematology and chemistry laboratory screening and Day 1 (Randomization) assessments must be at least 2 weeks apart, the screening duration is Day -35 to -14 days.

Table 2 On-Treatment Procedural Outline IM025006: Part 1, Treatment Period (Day 4 through Day 85)

Procedure/Vi sit Day	-	-	_	12-	week,	Doub	le-Bli	ind, Tı	eatme	ent Pe	eriod	_		-	Notes
(± 3 days for all visits unless	D 4ª	D 8	D 15	D 22	D 29	D 36	D 43	D 46 ^a	D 50	D 57	D 64	D 71	D 78	D 85	
otherwise noted)		W 1	W 2	W 3	W 4	W 5	W 6		W 7	W 8	W 9	W 10	W 11	W 12	
Safety Assessme	ents														
Concomitant medication use		X	X	X	X	X	X		X	X	X	X	X	X	Concomitant medications are medications taken any time after the first dose of study medication until the last study visit.
Monitor for AEs		X	X	X	X	X	X		X	X	X	X	X	X	Nonserious AEs must be collected from the time of the first dose of the study drug through the date of the follow-up or last visit. Monitoring for AEs will occur at every study visit.
Monitor for SAEs		X	X	X	X	X	X		X	X	X	X	X	X	All SAEs must be collected from the date of participant's written consent until 30 days after the final dose of the study drug or their participation in the study if the last scheduled visit occurs at a later time. Monitoring for SAEs will occur at every study visit.

Table 2 On-Treatment Procedural Outline IM025006: Part 1, Treatment Period (Day 4 through Day 85)

Procedure/Vi sit Day				12-	week,	, Doub	le-Bl	ind, Tı	reatme	ent Po	eriod				Notes
(± 3 days for all visits unless	D 4ª	D 8	D 15	D 22	D 29	D 36	D 43	D 46 ^a	D 50	D 57	D 64	D 71	D 78	D 85	
otherwise noted)		W 1	W 2	W 3	W 4	W 5	W 6		W 7	W 8	W 9	W 10	W 11	W 12	
Physical and M	etabo	olic A	Assessn	nents											
Full physical examination														X	A full examination will include general appearance, skin, head, eyes, ears, nose, throat, neck, thyroid, chest/lungs, heart, abdomen, lymph nodes, extremities, height, and body weight.

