Procedure/Visit Day (± 3 days for all	D 99	D 113	D 127	D 141	D 155	D 169	D 197 (± 7)	D 225	D 253 (± 7) EOS	ET	
visits unless otherwise noted)	W 14	W 16	W 18	W 20	W 22	W 24	W 28	W 32	W 36		
12-lead ECG									v	v	ECGs should be after the participant has been supine for at least
									X	X	5 minutes.
Liver biopsy										X	Liver biopsy must be carried out at the early termination visit only if the participant's prior liver biopsy occurred > 8 weeks prior to termination. See Section 8.6.1.1.

Table 3 On-Treatment Procedural Outline IM025006: Part 1, Follow-up Period (Day 99 through Day 253)

				24-w	eek, Fo	ollow-uj	p Period	l			Notes
Procedure/Visit Day (± 3 days for all	D 99	D 113	D 127	D 141	D 155	D 169	D 197 (± 7)	D 225	D 253 (± 7) EOS	ET	
visits unless otherwise noted)	W 14	W 16	W 18	W 20	W 22	W 24	W 28	W 32	W 36		
											MRE is to be performed ± 7 days of this day to allow sites scheduling flexibility. Participants must fast for 4 hours prior to MRE.
MRE						X			X	X*	* MRE must be conducted at the early termination visit only if the participant's prior MRE occurred > 4 weeks prior to termination. See Section 8.6.1.2.
Laboratory Assessn	nents										
Hematology	X		X		X			X	X	X	See Section 8.6.2.7 and Table 11.
Chemistry	X	X	X	_	X		X	X	X	X	See Section 8.6.2.7 and Table 11.

Table 3 On-Treatment Procedural Outline IM025006: Part 1, Follow-up Period (Day 99 through Day 253)

				24-w	eek, Fo	ollow-u _j	p Period	i			Notes
Procedure/Visit Day (± 3 days for all	D 99	D 113	D 127	D 141	D 155	D 169	D 197 (± 7)	D 225	D 253 (± 7) EOS	ЕТ	
visits unless otherwise noted)	W 14	W 16	W 18	W 20	W 22	W 24	W 28	W 32	W 36		
HbA1C									X	X	See Section 8.6.2.7 and Table 11.
Urinalysis	X		X		X			X	X		See Section 8.6.2.7 and Table 11.
Serum AFP					X			X	X		See Section 8.6.2.7 and Table 11.
Urine Pregnancy		X									For WOCBP only. See Section 8.6.2.1.5.
Pharmacokinetic			Sam	pling							
Blood PK sampling	X									X	Day 99: To be taken 3 weeks after last administration. See Section 8.6.3 and Table 12.

Table 3 On-Treatment Procedural Outline IM025006: Part 1, Follow-up Period (Day 99 through Day 253)

											1 (1)
				24-w	eek, Fo	ollow-uj	p Perioc	i			Notes
Procedure/Visit Day (± 3 days for all	D 99	D 113	D 127	D 141	D 155	D 169	D 197 (± 7)	D 225	D 253 (± 7) EOS	ET	
visits unless otherwise noted)	W 14	W 16	W 18	W 20	W 22	W 24	W 28	W 32	W 36		
Study Treatment/Pl	acebo	Admi	nistrat	tion (X	= BM	S-98626	$3;\mathbf{O}=1$	placebo)		

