Procedure/Visit Day (± 3 days for all visits unless	D 197 ±7 days	D 225	D 253 ±7 days EOS	ET	Notes
otherwise noted)	W 28	W 32	W 36		
Safety Assessments					
Concomitant medication use	X	X	X	X	Concomitant medications are medications taken any time after the first dose of study medication until the last study visit.
Monitor AEs	X	X	X	X	Nonserious AEs must be collected from the time of the first dose of the study treatment through the date of the follow-up or last visit. Monitoring for AEs will occur at every study visit.
Monitor SAEs	X	X	X	X	All SAEs must be collected from the date of participant's written consent until 30 days after the final dose of the study treatment or participant's participation in the study if the last scheduled visit occurs at a later time. Monitoring for SAEs will occur at every study visit.
Physical and Metabolic Assessn	nents				
Full physical examination			X	X	A full examination will include general appearance, skin, head, eyes, ears, nose, throat, neck, thyroid, chest/lungs, heart, abdomen, lymph nodes, extremities, height, and body weight.
Abbreviated physical assessment	X	X			Abbreviated examinations will include vital signs, weight, an abdominal exam, assessments of ascites and hepatic encephalopathy, and symptom-focused assessments.
12-lead ECG			X	X	ECGs should be after the participant has been supine for at least 5 minutes.

Table 6 On-Treatment Procedural Outline IM025006: Part 2, Follow-up Period (Day 197 through Day 253)

	12-week	κ, Follow-ι	ıp Period		
Procedure/Visit Day (± 3 days for all visits unless	D 197 ±7 days	D 225	D 253 ±7 days EOS	ET	Notes
otherwise noted)	W 28	W 32	W 36		
Liver biopsy				X	Liver biopsy must be carried out at the early termination visit only if the participant's prior liver biopsy occurred > 8weeks prior to termination. See Section 8.6.1.1.
					MRE is to be performed \pm 7 days of this day to allow sites scheduling flexibility. Participants must fast for 4 hours prior to MRE.
MRE			X	X	MRE must be conducted at the early termination visit only if the participant's prior MRE occurred > 4 weeks prior to termination.
					See Section 8.6.1.2.
Laboratory Assessments					
Hematology	X		X	X	See Section 8.6.2.7 and Table 11.
Chemistry	X	X	X	X	See Section 8.6.2.7 and Table 11.

Table 6 On-Treatment Procedural Outline IM025006: Part 2, Follow-up Period (Day 197 through Day 253)

	12-week	k, Follow-u	ıp Period		

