8.4.6.2 Discontinuation from the Study

Participants who request to discontinue study treatment will remain in the study and will continue to be followed for protocol specified follow-up procedures. The only exception to this is when a participant specifically withdraws consent for any further contact with him/her or persons previously authorized by participant to provide this information. Expectations are as follows:

- Participants should notify the investigator of the decision to withdraw consent from future follow-up in writing, whenever possible.
- The withdrawal of consent should be explained in detail in the medical records by the investigator, as to whether the withdrawal is from further treatment with study treatment only or also from study procedures and/or post treatment study follow-up, and entered on the appropriate eCRF page.
- In the event that vital status (whether the participant is alive or dead) is being measured, publicly available information should be used to determine vital status only as appropriately directed in accordance with local law.
- If the participant withdraws consent for disclosure of future information, the sponsor may retain and continue to use any data collected before such a withdrawal of consent.
- Assessments for the end of treatment/end of study visit must be performed, provided that the participant has not withdrawn consent for these activities.
- All required eCRF pages must be completed, including the date of and explanation for the withdrawal.
- As indicated, appropriate follow-up and/or alternate medical care must be arranged for the participant.

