8.6 Efficacy and Safety Assessments

Study procedures and timing are summarized in the Schedule of Activities (Section 1.2). Waivers or exemptions from protocol-required evaluations are not allowed.

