8.6.1.1 Liver Biopsy

Biopsies performed during screening for purposes of determining eligibility will be assessed by a local pathologist. Participants must have METAVIR Stage 3 or Stage 4 liver fibrosis to be eligible. If pathologic evidence suggesting a cause of liver fibrosis other than HVC-associated fibrosis is observed (eg, NASH), the participant is not eligible. If there is any question about the eligibility of a participant based on locally assessed biopsy results, the investigator should contact the medical monitor prior to randomizing the participant.

Tissue from biopsies performed during the study (or tissue submitted from prior biopsies when appropriate, see Section 8.1.1) will be collected for analysis. All histological assessments related to efficacy of BMS-986263 will be performed by a central reader. Details on the acquisition, quality requirements, histological preparation, and shipping of histological samples are in the Central Laboratory Manual. Due to the delay in assessing tissue samples for study endpoints, a report from the central pathologist will not be provided to the study sites. If

a clinical assessment of the biopsy is required a portion of the sample should be submitted to a local pathologist following the standard procedure utilized by the study site.

No more than 2 study associated biopsies will be conducted within a 48-week period. (Note: In some occasions the first pass for liver biopsy may not result in an adequate quantity of liver tissue, thus demanding for a second pass in order to obtain sufficient amount of liver tissue for analysis. The second pass should not be considered a second biopsy.)

To assess potential HSC suppression, the following assessments will be performed:

• Histology, including changes in hepatic architecture

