9.3.1 Efficacy

9.3.1.1 Efficacy Endpoints

The primary efficacy endpoint is the proportion of participants who achieve ≥ 1 stage improvement in liver fibrosis (METAVIR score) as determined by liver biopsy after 12 weeks of treatment in Part 1 and after 24 weeks in Part 2.

Secondary efficacy endpoints are as follows:

• Change in CPA, as compared to placebo after 12 weeks of treatment in Part 1 and after 24 weeks of treatment in Part 2

• Proportion of participants with ≥ 1 stage improvement in liver fibrosis (Ishak score), as compared to placebo after 12 weeks of treatment in Part 1 and after 24 weeks of treatment in Part 2

- Proportion of participants with ≥ 2 stage improvement in liver fibrosis (METAVIR score), as compared to placebo after 12 weeks of treatment in Part 1 and after 24 weeks of treatment in Part 2
- Proportion of participants with ≥ 2 stage improvement in liver fibrosis (Ishak score), as compared to placebo after 12 weeks of treatment in Part 1 and after 24 weeks of treatment in Part 2
- Proportion of participants with ≥ 15% decrease from baseline in liver stiffness as measured by MRE at Day 85 in Part 1 and Day 169 in Part 2
- Change from baseline in liver stiffness as measured by MRE Day 85 in Part 1 and Day 169 in Part 2

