5.10 Study Day

Study day is defined relative to the date of the first dose of study treatment. For assessments that occur on or after this visit date, study day is calculated as (assessment date – first dose date + 1). For assessments that occur prior to first dose date, study day will be calculated as (assessment date – first dose date); there is no Study Day 0. Study Day 1 is the day of first study treatment received.

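### The early-termination biopsy notes in Protocol Tables 3 and 6 can call for a third study biopsy, which the two-in-48-weeks limit in Section 8.6.1.1 forbids

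*Protocol*

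**What the plan says.** Each part has two scheduled biopsies: screening and Day 85 in Part 1 (Protocol 8.1.2), screening and Day 169 in Part 2 (Protocol 8.1.4).

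Section 8.6.1.1 sets the limit: "No more than 2 study associated biopsies will be conducted within a 48-week period". The only exception it gives is a second pass during the same biopsy.

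The follow-up tables in Section 1.2 list liver biopsy only in the ET column. Table 3 (Part 1) says "Liver biopsy must be carried out at the early termination visit only if the participant's prior liver biopsy occurred > 8 weeks prior" to termination. Table 6 (Part 2) applies the same condition: "prior liver biopsy occurred > 8weeks prior to termination". Both notes refer the reader to 8.6.1.1.

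Two general rules bear on how a site would act. Section 8.6 says "Waivers or exemptions from protocol-required evaluations are not allowed". Section 8.4.6.2 requires the end-of-treatment or end-of-study assessments "provided that the participant has not withdrawn consent for these activities".

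**The concern.** The ET condition depends only on time since the last biopsy. It does not ask whether the end-of-treatment biopsy has already been done. Someone with a study biopsy in screening and another at Day 85 or Day 169, who leaves more than 8 weeks after the second, meets the condition for a third. If all three fall within 48 weeks, a site that follows the table breaks 8.6.1.1, and a site that follows 8.6.1.1 omits a procedure the table requires.

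The extra biopsy would fall only on people leaving late in follow-up, since completers have none at Day 253. It also serves no visible primary or secondary endpoint. The histology endpoints in 9.3.1.1 are fixed at the end of treatment, for example "Change in CPA, as compared to placebo after 12 weeks of treatment in Part 1 and after 24 weeks of treatment in Part 2".

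**Working it through.** There is no statistical figure to reproduce; the check is calendar arithmetic.

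**Inputs**
- End-of-treatment biopsy: Day 85 or Day 169, visit window ±3 days (Tables 2 and 5).
- ET condition: more than 8 weeks, so at least 57 days, after the prior biopsy (Tables 3 and 6).
- Limit: 48 × 7 = 336 days (8.6.1.1).
- Last visit: Day 253 ± 7, so Day 260 at the latest (Tables 3 and 6).
- Screening: 35 days, extendable to 56 (8.1.1). Table 1, footnote a adds "The screening visit window may also be extended up to 5 additional days to accommodate unanticipated delays". Counting these on top of the 56 gives Day -61 as the earliest in-screening biopsy.
- Day count: SAP 5.10 says "there is no Study Day 0", so the span from Day -s to Day d is s + d - 1.

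**Step 1: when the ET condition is first met**
- Part 1: 85 + 57 = Day 142 (82 + 57 = 139 to 88 + 57 = 145 with the visit window).
- Part 2: 169 + 57 = Day 226 (166 + 57 = 223 to 172 + 57 = 229).

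**Step 2: span from screening biopsy to study end**

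| Screening biopsy | Last visit | Span | Weeks |
|---|---|---|---|
| Day -35 | Day 253 | 35 + 252 = 287 days | 41.0 |
| Day -56 | Day 253 | 56 + 252 = 308 days | 44.0 |
| Day -61 | Day 260 | 61 + 259 = 320 days | 45.7 |

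All are below 336 days. For a visit on Day 260, the limit stops binding only if the screening biopsy was more than 336 - 259 = 77 days before Day 1, that is, 78 or more. The stated screening limits do not allow that. So every third biopsy that follows two study biopsies under these rules falls inside the 48 weeks.

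**Step 3: who is not affected**
- Participants who leave before the end-of-treatment biopsy, or missed it: the ET biopsy is their second.
- Possibly those whose baseline was a routine-care biopsy taken before consent (allowed by 8.1.1), because that biopsy may not count as study-associated.

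**Step 4: how many could be exposed**

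The documents give no dropout rate for follow-up; the 10% in 9.1 concerns stopping treatment in Part 2. Assume a fraction r leaves evenly across follow-up, with r from 2% to 10%.
- Part 1: the window is Days 142 to 252 (111 days) out of Days 86 to 252 (167 days). 60 × r × 111/167 = 0.8 to 4.0.
- Part 2: the window is Days 226 to 252 (27 days) out of Days 170 to 252 (83 days). 120 × r × 27/83 = 0.8 to 3.9.

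These are upper illustrations. Consent withdrawal, loss to follow-up and missing end-of-treatment biopsies all reduce them.

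**The case against.** The best defence is that the two texts can be read together. Strictly, 'only if' states a necessary condition, and both notes send the reader to the section that holds the limit. On that reading the 8-week condition and the limit both apply, and no third biopsy is done. The note also has an evident purpose that causes no conflict: the on-treatment tables have no ET column, so these columns appear to serve everyone who terminates early, and for most the ET biopsy would be the second.

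That reading is possible but not the natural one. The note makes the biopsy mandatory, the MRE note beside it has the same form with a 4-week condition, and the same cross-reference appears on ordinary biopsy rows, where it signals no override.

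Several points do stand:
- The bar on waivers in 8.6 adds little, since keeping to a limit the protocol itself sets is not obviously a waiver.
- The affected group may be empty. It needs someone who leaves late, attends an ET visit, agrees to a biopsy and already has two study biopsies. Part 2 is itself conditional (8.3).
- A use for the later tissue in redacted text cannot be excluded. It would not remove the conflict with the limit.

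**Conclusion.** The concern holds. For participants with a study biopsy in screening and at end of treatment who terminate from about Day 142 (Part 1) or Day 226 (Part 2), the ET notes call for a third biopsy at most 320 days after the first, against a limit of two in 336 days, and no precedence is stated.

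The reach is small: at most about 1 to 4 participants per part under the assumed 2% to 10% loss, and possibly none. The primary result, power and error rate do not change. The reason to act is avoidable procedural risk from an invasive test, and the chance that some of the roughly 41 sites perform it while others do not.

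**What to change.** Amend the ET notes in Tables 3 and 6 so that a liver biopsy at ET is done only if all three conditions hold:
1. no post-baseline study biopsy has been obtained;
2. the prior biopsy was more than 8 weeks before termination;
3. the two-biopsy limit in Section 8.6.1.1 would not be exceeded.

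This keeps the ET biopsy for participants who left without an end-of-treatment sample and brings the maximum to two: screening plus Day 85 or Day 169, or screening plus ET.

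The cost is one clause in two table notes and the loss of a few late follow-up samples that no visible primary or secondary endpoint uses. The first condition is slightly wider than the limit needs, because it also rules out an ET biopsy after a routine-care baseline and an end-of-treatment biopsy. That does no harm to the visible analyses. If the sponsor wants those samples, conditions 2 and 3 alone would resolve the conflict.

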3. LIST OF ABBREVIATIONS AND DEFINITION OF TERMS

Term	Definition
AE	adverse event
AFP	alpha-fetoprotein
Anti-HB	hepatitis B surface antibody
Anti-HBc	hepatitis B core antibody
anti-HCV	hepatitis C virus antibody
ALP	alkaline phosphatase
ALT	alanine aminotransferase
AST	aspartate aminotransferase
BMD	bone mineral density
BMI	body mass index
BMS	Bristol-Myers Squibb
BUN	blood urea nitrogen
CFR	Code of Federal Regulations
CI	confidence interval
СМН	Cochran Mantel-Haenszel
CPA	Collagen Proportionate Area
Ctrough	trough observed plasma concentration
CYP	cytochrome P 450
CSR	Clinical Study Report
DDI	drug-drug interaction
DILI	drug-induced liver injury
DMC	data monitoring committee
DNA	deoxyribonucleic acid
dsDNA	double-stranded deoxyribonucleic acid
DXA	dual-energy X-ray absorptiometry
ECG	electrocardiogram
eCRF	electronic case report form

EOS	end of study
LOS	Chu of study
FDA	Food and Drug Administration
TDN	1 ood and Diag Administration
FSH	follicle stimulating hormone
GGT	gamma-glutamyl transferase
HbcAb	hepatitis B core antibody
HBsAb	hepatitis B surface antibody
HBsAg	hepatitis B surface antigen
HBV	hepatitis B virus
HBV core IgM	hepatitis B virus core-specific immunoglobulin mu antibody
HCC	hepatocellular carcinoma
HCV	hepatitis C virus
HIV	human immunodeficiency virus
HSC	hepatic stellate cell
IB	Investigator's Brochure
ICF	informed consent form
IEC	Independent Ethics Committee
Ig	immunoglobulin
IMP	investigational medicinal product
INR	international normalized ratio
IP	investigational product
IRT	interactive response technology
IV	intravenous
LDH	lactate dehydrogenase
LLN	lower limit of normal
MCH	mean corpuscular hemoglobin;
MELD	Model End Stage Liver Disease
mITT	modified intent-to-treat
MRE	magnetic resonance elastography
MRI	magnetic resonance imaging
NASH	nonalcoholic steatohepatitis
NOAEL	no observed adverse effect level
PCP	phencyclidine

PID	participant identification number	
PK	Pharmacokinetics	
PT	prothrombin time	
PTT	partial thromboplastin time	
QW	once every week	
Q2W	once every 2 weeks	
Q4W	once every 4 weeks	
RBC	red blood cell	
RNA	ribonucleic acid	
RNASEQ	RNA sequencing	
SAE	serious adverse event	
SAP	statistical analysis plan	
SLE	systemic lupus erythematosus	
SVR	sustained virologic response	
ULN	upper limit of normal	
WOCBP	women of childbearing potential	

Clinical Protocol IM025006 BMS-986263 HSP47 siRNA

4. ETHICS

4.1 Ethics Committee

This study will be conducted in compliance with institutional review board (IRB)/IEC and International Council for Harmonisation (ICH) Good Clinical Practice (GCP) guidelines and in accordance with applicable regulations regarding clinical safety data management (E2A, E2B[R3]) and scientific integrity (E4, E8, E9 and E10). In addition, this study will adhere to all local regulatory requirements and requirements for data protection.

Before initiating a study, the investigator must obtain written and dated approval from the IRB/IEC for the study protocol (and any amendments), written ICF, any consent form updates, participant recruitment procedures (eg, advertisements) and any written information to be provided to participants, and a statement from the IRB/IEC that these materials comply with GCP requirements. The approval must identify the protocol version as well as the documents reviewed.

4.2 Ethical Conduct of the Study

This study will be conducted in accordance with the Note for Guidance on GCP (ICH Harmonised Tripartite Guideline E6 (R1); FDA CFR [21 CFR § 50, 56, 312]), Declaration of Helsinki and all applicable regulatory requirements.

4.3 Participant Information and Consent

The investigator will explain the benefits and risks of participation in the study to each participant/legally acceptable representative in language readily understood by the participant. Written informed consent must be obtained before the participant enters the study and before any study-specific procedures are performed. If important new information becomes available requiring revisions to the ICF, the IRB/IEC-approved revised form will be used for reconsent of all participants.

